		Screening for MCI will occur under a separate protocol and elig be brought in for informed consent and study-specific				
Screening	Week -1	Visit 1	2 hours	Virtual*	Informed Consent & General Screening	
		Visit 1.1	30 minutes	NOVA Lab or LabCorp	Screening Blood Draw	74 mL (~5.0 TBL)
		Randomization Group A: NR or Group B: Placebo				
Baseline Testing	Week 0	Visit 2	3 hours	NOVA Lab	Vascular Testing	
		Visit 3	1.5 hours	Virtual*	Cognitive Testing	
		Visit 4	2 hours	CBBI	Neuronal Testing & Receive Capsules	
	Week 2	10 min Phone Check-In				
ion T	Week 4	Visit 5	0.5 hours	Virtual*	Zoom Check-In	
erventi Period	Week 6	10 min Phone Check-In				
Intervention Period	Week 8	Visit 6	0.5 hours	Virtual*	Zoom Check-In	
	Week 10	10 min Phone Check-In				
Follow-Up Testing	Week 12	Visit 7	3 hours	NOVA Lab	Vascular Testing	60 mL (~4.0 TBL)
		Visit 8	1.5 hours	Virtual*	Cognitive Testing	
		Visit 9	2 hours	CBBI	Neuronal Testing	
	Total Time		16 hours		Total Blood	134 mL (~9.0 TBL)

Brief Overview of Study Visits

not have access to a computer with video conferencing capabilities or upon the participant's request.

research team. All procedures and aspects related to the study including any potential risks will be

described to the subject. The investigator will read the informed consent form to the subject and will answer any questions that the subject may have prior to obtaining the subject's written consent. As documentation of the informed consent, the subject and the investigator performing the consent will sign the consent document and a copy of the signed consent form will be given to the subject. Alternatively, the consent may also be performed online via a private video conference and using the eConsent framework in REDCap. The video conferencing software is HIPAA-compliant and each scheduled online meeting will be secured with private meeting access controls, password protection, and end-to-end encryption so data in transit cannot be intercepted. The ability to provide informed consent will be monitored by the research team throughout the trial. In addition to obtaining written informed consent, all experimental procedures will be re-explained to the subjects at the time that they are performed, and verbal consent will be obtained.

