- **Total Cerebral Blood Flow** (CBF) will be assessed using extracranial high-resolution duplex ultrasound to capture both diameter and time-averaged MFV of the bilateral internal carotid arteries (ICA) and vertebral (VA) arteries (i.e., the two primary arteries that supply the brain)^{11–13}. CBF will be calculated for each artery as follows: CBF = MFV x π (diameter/2)² and summed in order to estimate total cerebral blood flow¹².
- **Neurovascular Coupling** will be assessed by measuring the Δ MFV_{MCA} and Δ MFV_{PCA} from 0 baseline in response to the progressively difficult N-back mental task of executive function and a repetitive visual stimulus^{14–16}. MFV_{MCA} and Δ MFV_{PCA} will be collected using TCD ultrasonography as described above. The N-back Cognitive Test measures working memory and executive function and activates areas of the brain supplied by the MCA. A computer program will display a series of numbers and the subject will be required to respond by clicking a button when the current number is identical to the same number N-trials previously. A control (0-back) level and two N-back levels will be performed. Numbers will be displayed with an inter-stimulus duration of one second with a 10-second pause between each level. Number sequence will vary between N-back conditions. The number of correct responses will be recorded to control for performance on the cognitive task itself. The repetitive visual stimulus activates the areas of the brain supplied by the PCA. A computer program will display a visual stimulus, as previously described. Briefly, the subject will be asked to focus their eves on a screen displaying an alternating black and white checkerboard stimulus for varied amounts of time (~40s each stimulus). The subject will be required to open and close their eyes when prompted by the research team.
- Post-testing blood sampling and urinalysis (visit 7 only). A urine sample and 4.0 Tablespoons of blood will be collected to repeat baseline blood measures (except for APOE genotype and B vitamins, which only need to be performed once).

VISITS 3 & 8: COGNITIVE FUNCTION (Virtual; 1.5 hour each)

Subjects will be instructed to refrain from taking over the counter medications for 48 hours, vigorous aerobic exercise and alcohol for 24 hours before testing. Subjects will be encouraged to eat a light meal or snack before coming to the lab.

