Intervention Administration. Placebo or NR capsules will be packaged and distributed by ChromaDex Inc. (under trade name, NIAGEN®) in individual containers. 12 weeks' worth of capsules will be administered to subjects by the research team at the beginning of the trial. Subjects will be provided with explicit instructions for dosing and frequency including instructions for missed doses.

Monitoring Adherence (pill count). Subjects will be instructed to bring their used and unused pill containers to the last post visit and, at which time a member of the research team will count the number of pills remaining in the container to assess adherence to the intervention.

Plan for Monitoring Adverse Events (AE's) and Serious Adverse Events (SAE's)

Adverse Event (AE): any untoward or unfavorable medical occurrence in a human study participant, including any abnormal sign (e.g. abnormal physical exam or laboratory finding), symptom, or disease,

temporally associated with the participants' involvement in the research, whether or not considered related to participation in the research.

Adverse Event Recording

The period for recording AE's will begin at the time of informed consent and will end at the time that the participant completes all testing, or is withdrawn from the trial. At each in-person or phone check-in, a blinded member of the study team will seek information from the participant on adverse events by specific questioning using a standardized physical symptom survey. Information on all AE's reported during the study period will be recorded immediately in the case report form (CRF). Adverse events will be described by duration (start and stop dates and times), severity, outcome, treatment and relation to study drug, or if unrelated, the cause, as described in the Data and Safety Monitoring Plan (DSMP).

Serious Adverse Event (SAE): any adverse event that:

- Results in death;
- Is life threatening, or places the participant at immediate risk of death from the event as it occurred;
- Requires or prolongs hospitalization;
- Causes persistent or significant disability or incapacity;
- Results in congenital abnormalities or birth defects;
- Is another condition which investigators judge to represent significant hazards.

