If a SAE occurs while the participant is on campus for a scheduled visit, the participant will be sent to the Christiana Care Medical Aid Unit ("Urgent Care") on the STAR Campus. If a participant contacts the laboratory or PI prior to seeking treatment for an ongoing AE or SAE, the participant will be directed to seek immediate medical treatment (e.g., visit their primary healthcare provider or, if requiring immediate attention, the nearest Urgent Care facility or Emergency Department). Any participant who is experiencing a life-threatening **medical emergency** will be instructed to call 911.

Reporting of SAE's

All participants experiencing a SAE will be instructed to notify the principal investigator after seeking immediate medical attention. As detailed in the Data and Safety Monitoring Plan (DSMP), all SAE's will be reported to the IRB, DSMB and other regulatory bodies (e.g., FDA, NIH) within 24 hours of the event being reported to the investigator. An expedited report of the SAE can be submitted by telephone, fax, or email and will be followed by a detailed, written SAE report as soon as possible. In the event that a participant calls the PI or another member of the study team prior to receiving treatment for an ongoing SAE, that participant will be instructed to seek immediate medical attention (e.g., visit urgent care).

Unblinding in Response to a SAE

All participants will be given a "Clinical Trial Participant Card" at the time of informed consent, which will provide the dates of their anticipated involvement in the study and important details regarding the active compound under investigation. The card will also provide a QR code to access the clinicaltrials.gov registry for this trial. Participants will be instructed to keep this card with them at all times (e.g., in their wallet) and to provide it to emergency personnel or other healthcare professionals if seeking treatment for an AE or SAE. In the event that emergency personnel or other healthcare professionals responding to a SAE determine that it is *medically necessary* to know the treatment to which a participant is randomized, the card will provide the contact information for the PI's office. PI will program their office line to forward all calls to their personal phone outside of normal business hours. In case of an emergency, the PI will be capable of breaking the blind for that participant.

STUDY TIMELINE

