- major psychiatric disorder (e.g. schizophrenia, bipolar disorder, major depression within past two years);

- neurological or autoimmune conditions affecting cognition (e.g. Parkinson's disease, epilepsy, multiple sclerosis, mild or severe traumatic brain injury, large vessel infarct);
- concussion within last 2 years and ≥ 3 lifetime concussions;
- current systemic medical illnesses, not including diabetes (e.g. cardiovascular disease, cancer, renal failure);
- prior history of any type of cancer other than basal cell carcinoma;
- substance abuse or dependence (DSM-V criteria);
- current use of medications used to treat dementia (e.g., anticholinesterase drugs) or other drugs likely to affect cognition (e.g., anticholinergic drugs, long-acting benzodiazepines);
- claustrophobia, metal implants, pacemaker or other factors affecting feasibility and/or safety of MRI scanning*;
- current smoking (including marijuana) within the past 3 months;
- hospitalization as a result of COVID-19.
- History of heart palpitations or arrhythmias

* In order to protect the health and safety of the participants, exclusion criteria for this study will include any contraindication to magnetic resonance scanning (e.g., metal in body, claustrophobia, pregnant). These exclusions are specific to MRI and are consistent with most studies involving MRI. Potential participants will be screened for the presence of any of these exclusion criteria prior to participating in this MRI study and before each MRI visit by having subjects complete an MRI screening form. **Describe what (if any) conditions will result in PI termination of subject participation.**

The primary exit criteria will include:

- completion of the study;
- failure to comply with the requirements of the study;
- lack of ability to continue to provide consent during the study;
- development of dementia during the study;
- treatment for impaired cognitive function by PCP;
- change in medication status that my affect primary outcomes (as determined by the PI);
- any serious adverse event that results in unblinding, prolonged disruption of the intervention or is deemed unsafe for the participant to continue in the trial.

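### Safety recording stops at withdrawal, with no questioning about later events and, for exits before Visit 7, no post-baseline safety bloods or urinalysis

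*Combined protocol and SAP*

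**What the plan says.** **Recording window.** Section 6, Adverse Event Recording, starts recording at consent and states that it "will end at the time that the participant completes all testing, or is withdrawn from the trial". Within that window a blinded team member goes through a standard symptom survey at each contact. The same paragraph sets what is recorded: "Adverse events will be described by duration (start and stop dates and times), severity, outcome, treatment and relation to study drug". It refers to the Data and Safety Monitoring Plan (DSMP) for how this is done.

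**Contacts and samples.** The Brief Overview of Study Visits shows contacts at weeks 2, 4, 6, 8 and 10. Weeks 2, 6 and 10 are each a "10 min Phone Check-In"; weeks 4 and 8 are half-hour video check-ins. None includes a blood draw. Under Visits 2 & 7 the laboratory repeat is headed "Post-testing blood sampling and urinalysis (visit 7 only"). Neither the visit table nor the payment table in section 9 lists an exit visit.

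**Exit rules.** Section 7 lists among its exit criteria "any serious adverse event that results in unblinding, prolonged disruption of the intervention or is deemed unsafe for the participant to continue in the trial". It adds dementia, loss of capacity, cardiovascular and metabolic events, major surgery and other serious changes in health. Leavers are replaced, and the number and reasons are documented. Stopping capsules and leaving the trial are not distinguished.

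**SAEs.** Under Reporting of SAE's, participants are told to notify the investigator, and the expedited report "will be followed by a detailed, written SAE report as soon as possible". That section sets no end date.

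**The concern.** Several of the reasons for leaving are themselves safety events, and leaving is what closes the recording window. Active collection can therefore stop in the people whose course after stopping the supplement is of most interest.

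Three items are at stake for a dosed participant who leaves early:

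- questioning about events after exit;
- a post-baseline laboratory value, if the exit is before Visit 7;
- the stop date and outcome of a non-serious event still open at exit, unless the DSMP provides for it.

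The laboratory item matters because section 6 (Visit 1.1) gives safety as one purpose of the bloods, and the protocol's definition of an adverse event includes abnormal laboratory findings. In someone who leaves before Visit 7, an on-study laboratory abnormality cannot be found. The gap cannot be filled later, because no sample exists. Section 8 also says that the arrhythmia risk of nicotinamide riboside is not known, which is a modest further reason to keep asking about symptoms for a few weeks.

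**Working it through.** **1. Is any other blood draw planned?** The visit table gives 74 mL at Visit 1.1 (before randomization), 60 mL at Visit 7 and a total of 134 mL.

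74 + 60 = 134 mL, and 5.0 + 4.0 = 9.0 tablespoons.

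The stated total is reproduced exactly and leaves no room for an interim or exit draw.

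**2. What is collected for someone who leaves before Visit 7?**

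| Item | Up to exit | After exit |
|---|---|---|
| Symptom survey | Yes, at each contact | None planned |
| Event that triggers exit, and reason for exit | Yes | Not applicable |
| SAE | Yes, with written report | Possible if the participant notifies; no active contact |
| Outcome of an open non-serious event | Required field | No contact in the protocol; the DSMP may cover it |
| Safety bloods and urinalysis | Before randomization only | None planned |

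Someone who leaves after Visit 7 but before Visit 8 or 9 already has the laboratory repeat. The laboratory point is therefore limited to exits before Visit 7.

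**3. How many people could this be?** Section 7 targets 58 participants and allows 25% for losses: 58 × 0.25 = 14.5, rounded up to 15, and 58 + 15 = 73. That 15 combines dropout, experimental failure, failed screening and conversion to dementia. The number who leave after a first capsule is not given.

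Assumption: 58 people have the Visit 7 sample, and *e* others leave after dosing and before Visit 7. Coverage = 58 / (58 + *e*).

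| *e* (assumed) | Dosed | Post-baseline safety bloods |
|---|---|---|
| 0 | 58 | 58/58 = 100% |
| 5 | 63 | 58/63 = 92.1% |
| 10 | 68 | 58/68 = 85.3% |
| 15 | 73 | 58/73 = 79.5% |

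The last row needs the whole allowance to be dosed people who leave before Visit 7.

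**4. How many contacts would be needed?** If exits are spread evenly over 12 weeks, the check-in at week *w* is missed with probability *w*/12. The mean number missed is (2 + 4 + 6 + 8 + 10)/12 = 2.5. Adding one call at week 12 gives 3.5 per leaver.

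- All by 10-minute phone call: 3.5 × 10 = 35 minutes.
- If weeks 4 and 8 keep their 30-minute length: 10 × (2 + 6 + 10)/12 + 30 × (4 + 8)/12 + 10 = 15 + 30 + 10 = 55 minutes.

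**The case against.** **Much is already recorded.** Symptoms up to exit, the event that triggers exit, the reason for it and a written report of each SAE are all planned. This stands. A reader might infer that events causing withdrawal, or serious events after it, are lost to the trial. The documents do not support that. What is missing is active questioning after exit; a later SAE depends on the participant coming forward.

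**The DSMP may deal with open events.** It is cited for how events are described and was not supplied; nor was the DSMB charter. This stands for the outcome of events already recorded, so that part is conditional. It does not remove the point about new events, because the protocol sets the end of recording itself.

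**The extreme is implausible.** People who fail screening never receive capsules, randomization precedes the first capsule, and an experimental failure need not mean a missing Visit 7 sample. The 79.5% is therefore a bound, not an expectation.

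**Lost time is not lost on-treatment time.** A reader might work out that 15 leavers, with exits spread evenly, lose (15 × 6)/(73 × 12) = 90/876 = 10.3% of planned recording time, and take this as missing on-treatment safety data. It is calendar time after exit. If capsules stop at exit, only delayed or post-stop events are missed.

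**An exit panel fills the gap only in part.** It is taken after the last capsule and may miss a change that reverses quickly. Neither a symptom call nor a blood panel measures heart rhythm, and section 7 already excludes people with a history of palpitations or arrhythmias. All of this stands and limits what the fix can deliver.

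**The pilot was reassuring.** Section 6 reports no SAEs and no change in liver or renal markers at this dose. That evidence is from 24 healthy older adults, not people with amnestic mild cognitive impairment.

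**Conclusion.** The point holds, with minor to moderate importance. The protocol states when recording ends, and its exit rules bring that end forward for some people because of a safety event. For dosed early leavers, no active questioning about later events is planned. For those who leave before Visit 7, no post-baseline bloods or urinalysis are planned. Subject to the DSMP, no contact is planned to close non-serious events open at exit.

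The size depends on a number that the documents do not give. Laboratory coverage of dosed participants lies between 100% and 79.5% for 0 to 15 such leavers, and the lower end is unlikely.

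A reader might infer that the comparison of adverse events between arms is biased, or that the cognitive results are affected. The documents support neither. They give no basis for expecting exits to differ by arm in a known direction, and no efficacy analysis uses these data for leavers. The case for change is that the missing safety information cannot be recovered later and costs little to collect.

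**What to change.** **1. Extend the window (section 6, Adverse Event Recording).** For everyone who took at least one capsule and agrees, record adverse events with the existing symptom survey, by 10-minute phone call, until the scheduled week-12 date. Follow events open at exit to resolution or stabilization. If the DSMP already does this, bring the protocol sentence into line with it.

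**2. Separate stopping capsules from leaving the trial (section 7).** Offer those who stop before Visit 7 the clinical panel and urinalysis already planned, as close to the last capsule as possible, in place of the Visit 7 draw. The LabCorp route allowed at screening would serve. Record days since the last capsule, and list these results separately from week 12. The date has to be asked for, because 12 weeks' "worth of capsules will be administered to subjects by the research team at the beginning of the trial" and the remaining pills are counted only at the last follow-up visit.

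**3. State who is counted.** Include withdrawn and replaced participants in descriptive by-arm counts of events and of exits by reason. The data are already recorded.

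**Cost.** About 35 minutes of calls per leaver, or about 55 if the week 4 and 8 check-ins keep their length. For 15 leavers that is 15 × 35 = 525 minutes (8.75 hours) or 15 × 55 = 825 minutes (13.75 hours). At the $9 per check-in in section 9, payments are 3.5 × $9 = $31.50 per leaver, or $472.50 for 15. Add at most one panel each in place of a missed draw, and a consent and IRB amendment that also settles whether people who have lost capacity may be contacted. Some leavers will decline.

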- Language. NIH Toolbox focuses on two aspects of language: vocabulary knowledge, which is fundamental to the growth of knowledge and which also has a very high association with overall intelligence, or what has been called the "g factor", and oral reading skill, which reflects level and quality of prior educational experiences, and provides a fairly robust indication of verbal intelligence that is relatively undisturbed by many medical conditions that affect the brain. Vocabulary language will be measured by the NIH Toolbox Picture Vocabulary Test while oral reading will be measured by the NIH Toolbox Oral Reading Recognition Test.
 - The NIH Toolbox Picture Vocabulary Test measures receptive vocabulary and is administered in a computerized adaptive format. The respondent is presented with an audio recording of a word and four photographic images on the computer screen and is asked to select the picture that most closely matches the meaning of the word.
 - During NIH Toolbox Oral Reading Recognition Test the participant is asked to read and pronounce letters and words as accurately as possible. The test administrator scores them as right or wrong. For the youngest children, the initial items require them to identify letters (as opposed to symbols) and to identify a specific letter in an array of 4 symbols. The test is given in a computerized adaptive format.

Visit 4: START Intervention (30 min; NOVA Lab)

 Receive 12-week supply of study pills (intervention instructions provided by member of research team)

VISITS 5 & 6: Bi-Weekly CHECK-IN Visits (Virtual or NOVA Lab*; 30 minutes)

Consult (bi-weekly). Brief check-in/consult with study coordinator (physical symptom survey);

 Patient-Reported Outcomes (PROMIS) Measures (monthly). Subjects will answer a brief battery of self-guided questionnaires (administered using an iPad, or online via REDCap) to determine their own perception of their health and well-being. Outcome measures will include: fatigue, pain, physical function, sleep disturbance, anxiety, depression, alcohol use, and social abilities. Subjects who cannot complete PROMIS measures online will report to the lab on a monthly basis to complete this measure.

OVERVIEW OF INTERVENTION (see attached Investigator's Brochure and Appendix for additional data)

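### The symptom survey is listed only at the five on-treatment check-ins (weeks 2 to 10), with none before the first capsule or at the week-12 visits, so new symptoms are judged on recalled onset dates and the last weeks of exposure have no scheduled query

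*Combined protocol and SAP*

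**What the plan says.** All of this is in protocol section 6 unless stated otherwise.

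- **Rule for asking.** Adverse Event Recording says: "At each in-person or phone check-in, a blinded member of the study team will seek information from the participant on adverse events", and that this is done "by specific questioning using a standardized physical symptom survey".
- **Contacts called check-ins.** The visit overview table uses the term for phone calls at weeks 2, 6 and 10 ("10 min Phone Check-In") and for Visits 5 and 6 at weeks 4 and 8. The compensation table in section 9 gives the label to the same five contacts.
- **Where the survey is listed.** The entry for Visits 5 and 6 reads "Brief check-in/consult with study coordinator (physical symptom survey". The listings for screening (Visits 1 and 1.1), baseline (Visits 2 to 4) and follow-up (Visits 7 to 9) do not name it.
- **Recording period.** "The period for recording AE's will begin at the time of informed consent and will end at the time that the participant completes all testing". Withdrawal also closes the period.
- **What is recorded.** "Adverse events will be described by duration (start and stop dates and times), severity, outcome, treatment and relation to study drug", with further detail left to the Data and Safety Monitoring Plan.
- **Exposure.** Capsules are handed out at Visit 4. Study Timeline says treatment goes on until the follow-up sessions are finished.

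**The concern.** The recording period is wider than the period in which anyone is scheduled to ask. This shows at both ends.

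At the start, no participant is listed to answer the survey untreated. The first scheduled answers come at week 2, on capsules. The side effects that section 8 names for NR are headache, warmth, flushing, gastrointestinal discomfort and fatigue. A person can have any of these before treatment. Deciding whether one is new or worse then depends on the participant remembering when it began and how bad it was, and section 7 enrols people because their memory is impaired.

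At the end, the longest exposure falls after the last scheduled survey. Section 8 also calls the risk of arrhythmia with NR unknown, which is a reason to keep asking until dosing stops.

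At stake is the quality of the safety description in a population new to this compound. The primary efficacy result is not affected.

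**Working it through.** The plan gives no figure on this point, so there is none to reproduce. The check is a count of contacts, a calculation of the gap, a comparison of the other safety sources, and the direction of any bias.

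**1. Count of scheduled surveys.** Check-ins fall at weeks 2, 4, 6, 8 and 10, which makes 5. Before the first capsule: 0. At week 12: 0.

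**2. Exposure after the last survey.** Gap = end of exposure − week 10.

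| End of exposure | Gap | Share of exposure |
|---|---|---|
| Week 12 (nominal) | 12 − 10 = 2 weeks | 2/12 = 16.7% |
| Week 13 (7-day testing period, or a 7-day delay) | 13 − 10 = 3 weeks | 3/13 = 23.1% |
| Week 14 (both) | 14 − 10 = 4 weeks | 4/14 = 28.6% |

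The nominal figure is the main one. The other two assume that dosing continues to the final session, as Study Timeline says, although only a 12-week supply is handed out. The delay is allowed only when there is a scheduling conflict or illness.

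**3. What else covers the two ends.**

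- *PROMIS* is taken at Visit 1 and listed again under Visits 3 and 8. The label there is Visit 12; no such visit exists, and I read it as week 12. Of the five side effects named in section 8, its stated domains include one, fatigue. Headache, warmth, flushing and gastrointestinal discomfort are not named.
- *Medical history* at Visit 1 is taken to check eligibility. It is not described as a graded list of current symptoms.
- *Blood and urine tests* are repeated at Visit 7. They do not detect headache or flushing.
- *Unsolicited reports* are recorded throughout, because the recording period is open.

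So there is partial cover at both ends, but no like-for-like symptom answer at either.

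**4. Direction of any misclassification.** Let b be the share of each arm with the symptom before treatment, and c the share of those wrongly dated as new. Let p be the true rate of new symptoms in an arm, independent of background. Then

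observed rate = 1 − (1 − bc)(1 − p),

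and the observed difference between arms = (1 − bc) × the true difference.

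Randomization makes b similar in the two arms, and blinding does the same for c, so the factor is common to both and the difference shrinks. If recall is perfect, c = 0 and nothing is lost. Assumed values of bc of 0.10, 0.20 and 0.30 leave 90%, 80% and 70% of the true difference. The documents give neither b nor c, so this shows direction only and is not an estimate.

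**The case against.** **The text is silent; it does not exclude.** A reader might infer that the survey is ruled out at baseline and week 12. The documents do not say so. The recording rule mentions in-person check-ins, and the overview table labels every check-in as phone or video, so the phrase could be meant to cover all in-person visits. Against that, the heading "VISITS 5 & 6: Bi-Weekly CHECK-IN Visits (Virtual or NOVA Lab*; 30 minutes" shows that Visits 5 and 6 may be held at the lab, so the phrase has a meaning without the other visits. Staff working from the visit listings would not give the survey at baseline or week 12. The ambiguity stands, and it needs settling.

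**Existing symptoms need not be counted as events.** A reader might also infer that any complaint present before treatment becomes an adverse event. That does not follow. Start dates, severity and relation to the study drug are recorded, so a headache that began before the first capsule can be dated as such. What remains is that the date is recalled, with no untreated answer to set it against.

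**The size is unknown.** It is tempting to assume new-symptom rates of 20% on NR and 5% on placebo, with 10% to 30% background all counted as new. The risk ratio then falls from 4.0 to between 1.9 and 1.3, and the difference from 15 points to between 13.5 and 10.5. Those rates have no source in the documents, and the scenario ignores the recorded onset dates. The pilot table in section 6 shows headache 4 times on placebo and 0 on NR, and flushing or hot flashes 2 times and 1 time. Section 10 plans no test of adverse events between arms.

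**Other documents may settle it.** The monitoring plan, the DSMB charter and the symptom questionnaire are cited but are not part of the text reviewed. They may define treatment-emergent events or set a recall period. This is fair. Even so, the visit listings are what staff follow, and they should agree with those documents.

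**Conclusion.** The point holds as a gap in scheduled ascertainment. On the visit listings there are 5 surveys, all on treatment, with none before the first capsule and none after week 10. The gap at the end is nominally 2 of 12 weeks, and at most 4 of 14 if dosing runs through an extended and delayed testing period.

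The consequence is limited. Pre-existing and new symptoms can be told apart, but only through recall in people with memory impairment. The last weeks are covered in part by PROMIS, laboratory tests and unsolicited reports. Any misclassification should be alike in both arms and would tend to dilute a difference rather than favour an arm. No figure can be put on it from the documents.

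This rests on reading check-in as the visit overview and compensation table use the word. If the protocol means every in-person visit, the procedure is sound in intent and only the listings need correcting.

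**What to change.** Add the existing symptom survey at two points and name it in the visit listings:

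1. **Before the first capsule**, for example at Visit 4, where capsules are handed out.
2. **At the last week-12 session attended.** Tie this to whichever session comes last, not to Visit 9. Study Timeline lets the order of visits change, and section 9 says participants without a baseline MRI are not scheduled for the follow-up one.

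This raises the scheduled surveys from 5 to 7 and closes the gap after week 10. Amend Adverse Event Recording to match, and state there that symptoms new or worse than the pre-treatment survey are summarised by arm as treatment-emergent. Check that the Data and Safety Monitoring Plan uses the same definition.

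The cost is two more uses of a short questionnaire at visits already attended, plus a line in the visit listings and one in Adverse Event Recording.
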